If a patient was prematurely withdrawn from the study prior to Week 72, all assessments scheduled for Visit 11 were to be performed at the time the patient withdrew. If a patient participating in the optional extension study withdrew prior to commercial drug availability, all assessments scheduled for the optional extension period EOT visit were to be performed.

If a liver biopsy was performed according to the local regulations or standard of care at any time during A4250-008, the biopsy results should have been recorded in the electronic case report form (eCRF). If liver biopsy results were collected for a patient in Study A4250-005 or prior to Week 24 in Study A4250-008, the patient was to be asked to consent to a follow-up liver biopsy at Visit 11, if allowed per local regulations, unless 2 prior liver biopsy results had been collected (with at least 1 year between biopsies). Liver biopsies were not performed in Spain.

For patients not participating in the optional extension period, Visit 12 was to take place 28 days after Visit 11. All patients who were prematurely withdrawn were to have this visit 28 days after the last dose of study drug for AE monitoring and other safety follow-up assessments.

If a patient discontinued before Week 72, additional telephone contacts were to be made every 3 months after the Follow-up visit (Visit 12) up to Week 72 to inquire whether the patient had undergone biliary diversion or liver transplantation, and if ongoing TEAEs at the time of discontinuation had resolved. The telephone calls were to take place up until 72 weeks even if the patient had biliary diversion or liver transplant.

Patients and/or caregivers were instructed to complete the electronic diary (eDiary) every morning and evening for the first 24 weeks (Visits 1 to 5) and for the 21 days before each clinic visit thereafter (Visits 6 to 12). In addition, Cohort 2 patients and/or caregivers were instructed to complete the eDiary during the Screening period. Patients participating in the optional extension period were not to complete eDiary entries after Visit 11. The eDiary included patient-reported outcome (PRO) and observer reported outcome (ObsRO) items for evaluation of itching (using PRO), scratching (using ObsRO), and

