4.4 Safety Evaluation

Safety criteria are as follows:

- The primary safety analysis for this study will include the incidence of total treatment-emergent adverse events (TEAEs) and TEAEs categorised by causality, severity, and seriousness assessments made by the Investigator.
- Trends in safety will also be evaluated for the following:
 - Physical examinations
 - Concomitant medications
 - Vital signs
 - Laboratory test results (including clinical chemistry, haematology, urinalysis, alfa-fetoprotein [AFP], vitamins A and E, 25-hydroxy vitamin D, and INR)
 - Abdominal ultrasound
 - Discontinuations due to AEs

5. Sample Size and Power

There is no formal hypothesis testing in this open-label study. The sample size for Cohort 1 was determined in Study A4250-005. For Cohort 1, patients will be enrolled after completion of Study A4250-005 or participation of 12 weeks in that study. For the other endpoints, mainly descriptive analyses will be performed.

The proportion of patients with at least 1 event (i.e., surgical bile diversion, liver transplantation, death) that can be expected in a non-treated population depends on PFIC type and age distribution of the included patients. The expected proportion of patients with events will be calculated for the study population once each patient's age and PFIC type are known, using the probability that a patient will get an event estimated from the reference population in the ongoing observational cohort study, NAtural Course and Prognosis of PFIC and Effect of Biliary Diversion (NAPPED).

As an example, if the expected proportion of patients with at least 1 event is estimated to be 30% in the study population, and then if the proportion of patients with at least 1 event during odevixibat long-term treatment is shown to be only 10% in the study, the power is approximately 89% to 96% (1-sided test, alpha=2.5%) for a confidence interval (CI) with upper boundary <30% based on a sample size of n=48 to 60. The sample size of 60 for Cohort 2 was estimated based on the availability of target patient population to evaluate the therapeutic benefit for those patients.

6. Interim Analysis

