⁸ <https://www.cdc.gov/nccdphp/dnpao/growthcharts/resources/sas-who.htm> following WHO's method

⁹ Abdel-Rahman, Susan M et al. "Construction of Lambda, Mu, Sigma Values for Determining Mid-Upper Arm Circumference z Scores in U.S. Children Aged 2 Months Through 18 Years." *Nutrition in clinical practice* : official publication of the American Society for Parenteral and Enteral Nutrition vol. 32,1 (2017): 68-76.

The number and percent of patients achieving positive pruritus assessment for more than 50% of the time will be summarised by treatment group. Both AM and PM pruritus assessments will be included in the analysis of this endpoint. A cumulative distribution function (CDF) plot showing proportions of patients achieving positive pruritus assessment for more than X% of the time, X is the time of achieving positive pruritus assessment from 0 to 100%, by treatment group will be provided.

❖ Proportion of Responders for Pruritus Scores

The proportion of responders for pruritus scores will be tabulated by visit based on monthly scores and bi-weekly scores. The 95% CI of the proportion of responders will be provided, based on the exact method of Clopper-Pearson. A responder is defined as a patient who reports a decrease in pruritus score from unrounded baseline equivalent to or greater than the threshold of meaningful change estimated from the blinded psychometric analysis; the results of the blinded psychometric analysis across all anchors support a threshold of 1.0 point for AM, PM and AM and PM scratching scores. Baseline 1 and 2, defined in the table of derived variables in [Appendix A](#), will be used for data analysis. Baseline 1 will only be used for patients in Cohort 1 who were on odevixibat in Study A4250-005.

❖ Biliary Diversion Surgery and Liver Transplantation

Number and percent of patients undergoing biliary diversion surgery and/or liver transplantation will be summarised by using descriptive statistics. A 95% CI also will be presented for the corresponding percentage. These parameters will be evaluated separately and together at Weeks 24, 48, 72 and all visits (every 16 weeks) during the optional extension period.

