Kaplan-Meier curves will be used when appropriate for time-to-event data (that is, time to biliary diversion surgery or liver transplantation or death and time to any event). If a patient does not have any event, the patient will be censored at the last contact date. Median event-free times and associated 95% CIs will be calculated using Brookmeyer and Crowley methodology and a log-log transformation for constructing CIs.

❖ Fibroscan®

The change in APRI and Fib-4 score will be summarised using descriptive statistics from baseline 2 to Week 72 and all visits (every 16 weeks) during the optional extension period.

❖ PELD and MELD Score

The change in PELD and MELD will be summarised separately using descriptive statistics from baseline 2 to Week 72 and all visits (every 16 weeks) during the optional extension period.

❖ UDCA and/or Rifampicin

Percentages of patients in use of UDCA and/or Rifampicin at weeks 24, 48, and 72 will be presented in 4 categories, use of UDCA, use of Rifampicin, use of UDCA or Rifampicin, use of UDCA and Rifampicin. Percentage will be based on patients in study at week 24, 48, and 72.

Shift tables from Baseline 2 in use of UDCA and/or Rifampicin at Weeks 24, 48, and 72 will be presented in the following categories. “None”, “UDCA alone”, “Rifampicin alone”, “UDCA and Rifampicin”, “Early Termination”. Percentage will be based on patients in study at week 24, 48, and 72.

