TEAEs (number of patients with any events and number of events, if applicable) by SOC and PT in each treatment group will be tabulated for the following:

- TEAEs by SOC and PT including fat-soluble vitamin deficiencies, diarrhoea, hepatotoxicity (as defined in Section 9.7.1.1). Note that hepatotoxicity will also be included with the tabulation of hepatic events
- All TEAEs by preferred term by descending incidence in Overall column
- TEAEs leading to study discontinuation by SOC and PT
- Serious TEAE by SOC and PT
- Drug-related serious TEAE by SOC and PT
- TEAEs leading to death by SOC and PT
- Common TEAEs ($\geq 10\%$ in overall)
- Hepatic TEAEs
 - a. Liver-related TEAEs (events that, per the Investigator, are considered related to PFIC) by SOC and preferred term
 - b. Suspected DILI events (as adjudicated by the DSMB and defined in [Section 9.7.1.2](#))
 - c. TEAEs of liver decompensation (as defined in Section 9.7.1.2) by SOC and preferred term
 - d. Drug related hepatic disorders – comprehensive search SMQ (narrow and broad)

Summary tables for the number of patients with any TEAEs by SOC and PT by severity (mild, moderate, severe) and by causality (related [possibly, probably and definitely] versus unrelated [unlikely and unrelated]), will also be provided during the treatment period. AEs with the worst severity will be used in the by-severity summaries. Similarly, AEs with the worst causality (related to treatment) will be used in the by-causality summaries. If severity or causality is missing, data will be imputed to the worst category.

Where a patient has the same AE, based on PT, reported multiple times in the treatment period, the patient will only be counted once at the PT level in AE frequency tables.

Where a patient has multiple AEs within the same SOC in the treatment period, the patient will only be counted once at the SOC level in AE frequency tables.

In the AE summaries, AEs will be sorted alphabetically by SOC and PT. In addition, the numbers of patients with liver-related mortality, liver-decompensation events, and all-cause mortality will be presented using descriptive statistics. Kaplan-Meier curves may be used for time-to-event data (time taken to experience liver-decompensation event, all-cause mortality, and biliary diversion surgery in weeks).

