9.8.2 Data Safety Monitoring Board

The DSMB will receive data in the form of tables, figures, and listings (provided by unblinded DSMB statistician from Firma who is independent to the Firma study team). The requirement for blinded or unblinded data is defined in the DSMB charter. Data provided to the DSMB will include, but is not limited to, demographics, baseline characteristics, medical and surgical history, prior and concomitant medications, AE and SAE data (by SOC and PT and by maximum intensity), laboratory data, liver monitoring, vital sign measurements, and abdominal ultrasound and patient disposition data.

10. Changes to Planned Analysis from Study Protocol

The changes to the planned analysis in the protocol are listed below.

1. Endpoints
 - a. Removed below secondary efficacy endpoints
 - i. All-cause mortality
 - ii. Change in use of antipruritic medication at Weeks 24, 48, and 72
 - b. Added below secondary efficacy endpoints
 - i. Change in use of UDCA and/or Rifampicin at Weeks 24, 48, and 72
 - ii. Proportion of responders for pruritus scores

- c. Added below exploratory endpoint
 - i. Change from baseline in episodic flares during the study treatment for BRIC patients.
- d. Added below safety endpoint
 - i. All-cause mortality
- e. Updated secondary and exploratory efficacy endpoints to add the visits during extension period

2. Data Analysis

- a. For the number of patients with events (biliary diversion surgery or liver transplantation or death) and time to event, the comparison to the NAPPED population will be not included in this SAP and will be performed separately.
- b. The following analysis in the protocol “As an exploratory analysis of pruritus and serum bile acids, a comparison of treatment with A4250 120 µg/kg/day during the first 24 weeks of Study A4250-008 versus placebo patients over the 24 week treatment period from Study A4250-005 will be carried out.” was conducted in A4250 ISE analysis because Study A4250-008 did not have post-baseline data of Study A4250-005.
- 3. TEAE definition is updated from “during treatment period” to “during treatment period and within 28 days follow-up after the last dose”.
- 4. Laboratory data will only be considered up to 14 days follow-up after the last dose of Odevixibat for efficacy related endpoints.
- 5. For any hepatic TEAEs, add “Drug related hepatic disorders – comprehensive search SMQ (narrow and broad)”.

11. Appendices

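### Single-event Kaplan-Meier curves for diversion, transplantation and decompensation have no rule for patients who die or are transplanted first

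*SAP*

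**What the plan says.** Section 9.6.4 plans time-to-event displays for the surgical outcomes in conditional terms: "Kaplan-Meier curves will be used when appropriate for time-to-event data", with the endpoints given as "that is, time to biliary diversion surgery or liver transplantation or death and time to any event". The one censoring rule follows: "If a patient does not have any event, the patient will be censored at the last contact date".

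Section 9.7.1 says that Kaplan-Meier curves may also be used in the safety analysis, for "time taken to experience liver-decompensation event, all-cause mortality, and biliary diversion surgery in weeks". It adds no censoring rule.

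The main summary of diversion and transplantation in Section 9.6.4 is a number and percent with a 95% confidence interval: "These parameters will be evaluated separately and together at Weeks 24, 48, 72" and at the extension visits. Section 10 uses the three-event phrase again: "For the number of patients with events (biliary diversion surgery or liver transplantation or death) and time to event".

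On follow-up of patients who discontinue before Week 72, Section 3.1 says: "The telephone calls were to take place up until 72 weeks even if the patient had biliary diversion or liver transplant". No section names cumulative incidence or any other competing-risk method.

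**The concern.** A patient who has died cannot later have a diversion, a transplantation or a decompensation event. A transplanted patient is, for analysis purposes, no longer at risk of diversion or of decompensation of the native liver. Kaplan-Meier with such patients censored treats them as if they could still have the event later, at the rate of those still at risk. One minus Kaplan-Meier then estimates an incidence in a setting where death and transplantation do not occur, and it lies above the proportion of patients who actually have the event.

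The SAP does not say that these patients are censored at the other event. It gives no handling at all, so the choice falls to the programmer after the data are in. The same report will carry crude percentages for diversion and transplantation, so a reader could see a curve and a percentage that differ with no explanation.

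**Working it through.** **Which curves are planned.**
- In Section 9.6.4, if the three-event phrase were already the composite, the words about any event would name it a second time. Component curves plus a composite is therefore the more natural reading.
- Section 10 uses the same three events with a single time to event, which reads as one composite. Section 9.6.4 is thus ambiguous.
- Section 9.7.1 is not ambiguous on two events: decompensation alone and diversion alone are named as possible curves.

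**What the censoring rule covers.** Read literally, it applies to patients with no event of any kind. If it is instead read as applying to each curve's own event, a patient who dies is censored at a last contact no later than death, which is ordinary censoring. A transplanted patient would stay in the diversion risk set until last contact, which gives a different estimate. The text does not choose between these readings.

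**The plan's own figure.** Section 5 gives an example in which "if the expected proportion of patients with at least 1 event is estimated to be 30% in the study population", against 10% on odevixibat, with power of 89% to 96% for n=48 to 60 (one-sided 2.5%). With an exact Clopper-Pearson upper limit below 30% and a true proportion of 10%:
- n=48: met with at most 7 events; P(X ≤ 7) = 89.8%.
- n=60: met with at most 10 events; P(X ≤ 10) = 96.6%.

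The stated power reproduces. It concerns the composite and is not in dispute. Its 10% and 30% serve below as composite event proportions.

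**Size of the excess.** Assume constant hazards. The SAP gives no split between events, so two are assumed for diversion/transplantation/death: equal thirds, and 60/30/10.

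For composite proportion C and share f:
- total cumulative hazard H = −ln(1 − C), so H = 0.1054 at 10% and 0.3567 at 30%;
- one minus Kaplan-Meier, others censored = 1 − exp(−fH);
- cumulative incidence as first event = fC.

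| C | Split | Event | 1−KM | Cumulative incidence | Excess (points) |
|---|---|---|---|---|---|
| 10% | equal | each | 3.45% | 3.33% | 0.12 |
| 10% | 60/30/10 | diversion | 6.13% | 6.00% | 0.13 |
| 10% | 60/30/10 | transplantation | 3.11% | 3.00% | 0.11 |
| 10% | 60/30/10 | death | 1.05% | 1.00% | 0.05 |
| 30% | equal | each | 11.21% | 10.00% | 1.2 |
| 30% | 60/30/10 | diversion | 19.27% | 18.00% | 1.3 |
| 30% | 60/30/10 | transplantation | 10.15% | 9.00% | 1.1 |
| 30% | 60/30/10 | death | 3.50% | 3.00% | 0.5 |

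Over all rows the range is about 0.05 to 0.13 points at 10% and 0.5 to 1.3 points at 30%. The low ends are the death rows. They would apply only if follow-up for death were cut at surgery, so they do not measure a bias in all-cause mortality properly counted.

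**Transplantation with only death competing.** Diversion does not in itself prevent a later transplantation. With shares f_T for transplantation and f_D for death, cumulative incidence = f_T/(f_T + f_D) × [1 − exp(−(f_T + f_D)H)]. This assumes that diversion leaves the transplantation hazard unchanged.
- Equal shares, C=10%: 0.5 × (1 − exp(−0.0702)) = 3.39% against 3.45%, an excess of 0.06 points.
- Equal shares, C=30%: 0.5 × (1 − exp(−0.2378)) = 10.58% against 11.21%, an excess of 0.6 points.
- 60/30/10, C=10%: 0.75 × (1 − exp(−0.0421)) = 3.10% against 3.11%, an excess of 0.02 points.
- 60/30/10, C=30%: 0.75 × (1 − exp(−0.1427)) = 9.97% against 10.15%, an excess of 0.2 points.

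For decompensation the SAP gives no event rate, so no figure is offered.

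**The case against.** The strongest reply is that the SAP never states the faulty analysis. No section censors a patient at death, diversion or transplantation. Section 9.6.4 can be read as the composite alone, as Section 10 reads, and both Kaplan-Meier statements are conditional. This stands as far as it goes: the point is an omission and an ambiguity, not a stated error. It does not remove the point, because Section 9.7.1 names two single-event curves and optional use does not supply the missing rule.

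A reader might infer that every incidence is overstated. The documents do not support that. Death remains observable after diversion or transplantation. For early discontinuers, calls continue to Week 72 after either procedure, and Section 8.1.1 exempts the surgery analysis from its exclusion of later data. All-cause mortality is not inflated if those deaths are counted. The composite has no competing event among its own components, and the crude percentages are not Kaplan-Meier estimates.

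A reader might also infer that the comparison with the natural-history cohort is compromised. Section 10 places that comparison outside this SAP, and Section 5 frames it on the proportion with at least one event, which is the composite.

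Nor would component incidences that sum to more than the composite prove bias. One patient can have a diversion and later a transplantation.

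**Conclusion.** The point holds for single-event curves of non-fatal outcomes: decompensation and diversion under Section 9.7.1, and diversion and transplantation if Section 9.6.4 means component curves. The handling of a patient who dies or is transplanted first is not stated, and ordinary censoring would bias these incidences upward.

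The size is minor. For diversion the excess is about 0.12 to 0.13 points at a 10% composite and 1.2 to 1.3 points at 30%. For transplantation it is no larger, and it is smaller when only death competes. These figures rest on constant hazards, on assumed splits, and on censoring that the SAP does not spell out. In a mainly descriptive open-label study this is a worthwhile clarification and no threat to the main conclusions.

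**What to change.** In Sections 9.6.4 and 9.7.1, state for each curve whether it is composite or single-event, and how a patient with a different event is handled.

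- Keep Kaplan-Meier for the composite of diversion, transplantation or death, and for all-cause mortality, counting deaths after surgery.
- For diversion, transplantation and liver decompensation alone, report Aalen-Johansen cumulative incidence with death as a competing event.
- For diversion and decompensation, treat transplantation as competing too.
- Do not treat diversion as competing with transplantation or death.

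The cost is a few sentences and a standard option in the planned software. No additional data are needed.

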9.6.5 Analyses of Exploratory Endpoints

The exploratory efficacy variables are listed in [Section 4.3](#). All exploratory analyses mainly will be summarised descriptively based on the FAS, unless otherwise specified.

Exploratory variables including ALT; GGT; total bilirubin; INR; albumin; liver enzymes; leukocytes and platelets; measures of bile acid synthesis; Albireo PRO and ObsRO itching/scratching severity scores; Albireo PRO and ObsRO sleep parameters; Global Symptom Relief; and PedsQL will be summarised descriptively. For continuous data, the change from baseline will be analysed in addition to the presentation of actual visit values. For categorical data, shift tables or frequency and percentages of patients will be presented, as appropriate. A line graph of itching/scratching daily severity scores of Albireo PRO and ObsRO over time will be provided for each patient.

For continuous data, such as ALT; GGT; total bilirubin; INR; albumin; liver enzymes; leukocytes and platelets; measures of bile acid synthesis; and the total score and domain score of PedsQL, the change from baseline 2 will be analysed descriptively in addition to the actual visit values. Global Symptom Relief at Weeks 4, 12, 24, 48, 72 and all visits (every 16 weeks) during the optional extension period will be summarised as categorical variables. Time points (visit windows) are specified in [Appendix B](#).

❖ Proportion of Positive Pruritus

The proportion of individual assessments meeting the definition of a positive pruritus assessment at the patient level on the Albireo PRO instrument completed by patients ≥ 8 years of age only will also be explored and summarised in a similar fashion as for the secondary endpoint, the proportion of individual assessments meeting the definition of a positive pruritus assessment at the patient level on the Albireo ObsRO instrument.

Change from baseline 2 in PRO/ObsRO itching and scratching severity scores will be summarised by each 4-week interval between Visit 1/Screening and Visit 5/Week 24, then by each visit between Visit 5/Week 24 and Visit 12/Week 76. A summary table will be provided for night-time scores and morning time scores separately.

The pooled pruritus score including observer-reported scratching for patients < 8 years of age and patient-reported itch severity for patients ≥ 8 years of age will be summarised in a similar manner.

The change from baseline 2 in PRO/ObsRO sleep parameters will be summarised at Week 72 as well as by each 4-week interval between Visit 1/Screening and Visit 5/Week 24, then by each visit between Visit 5/Week 24 and Visit 12/Week 76. Sleep parameters include difficulty of falling asleep and staying asleep, tiredness, and the number of awakenings.

❖ Fibroscan®

Change from baseline 2 in stage of liver fibrosis measured by Fibroscan® will be analysed descriptively. The frequencies of stages will be summarised by shift tables. Steatosis grade analysis will be performed in a similar fashion. Liver fibrosis as assessed by post-treatment biopsy will be listed and change from baseline may be presented, if available.

❖ Episodic Flares

Due to limited data availability and only 4 BRIC patients were enrolled in the study, the episodic flares data during the study will be presented as a listing.

